13.4.2 Secondary Endpoint Analyses

The secondary endpoints are the WOMAC A1 walking pain change from baseline at each post-baseline time point: 2, 4, 8, and 16 Week. Each of the secondary endpoints will be analyzed utilizing the primary longitudinal model described in the Primary Endpoint Analysis (Section 13.4.1). A gate-keeping procedure will be implemented to control the family-wise Type 1 Error (see Section 6.1), thus the secondary endpoints will be tested in sequence only provided as a statistically significant result was obtained in the previous test.

If any of the sensitivity analyses conducted on the primary endpoint produces results which differ substantially from the primary analysis, the sensitivity analyses will be repeated on all secondary endpoints.

13.4.3 Additional Efficacy Analyses

No additional efficacy analysis of the primary and secondary endpoints is planned; tertiary endpoint analyses are described in Section 13.8.

13.5 Safety Evaluations

The safety of the therapy will be assessed by comparing the incidence of adverse events in the MONOVISC group vs the Saline group through 26 weeks post-injection, including AEs that occur during injection. In addition, the number and percentage of subjects with adverse events will be reported.

13.5.1 Adverse Events

An Adverse Event (AE) is any untoward medical occurrence in a subject, regardless if there is a relationship between the adverse events and the study devices.

At each evaluation of the subject enrolled in a clinical investigation, the Investigator determines whether any A) have occurred, and determines their relationship to the study devices or procedure.

All adverse events, study device malfunctions and other product issues must be recorded in the medical records and entered into CRFs. There are immediate post-injection or peri-injection events that are changes from the baseline condition of the Subject, but are expected events resulting from the treatment. If these events occur, they should be recorded in the Subject's medical record.

An Unanticipated Adverse Device Effect (UADE) is defined as any serious adverse effect on health or safety or any life-threatening problem or death caused by, or associated with, a device, if that effect, problem, or death was not previously identified in nature, severity, or degree of incidence in the investigational plan or application (including a supplementary plan or application), or any other unanticipated serious problem associated with a device that relates to the rights, safety, or welfare of subjects.

Serious Adverse Events (SAEs) are defined as any AE that:

- 1) Led to a death;
- 2) Led to a serious deterioration in the health of the subject that:
 - Resulted in life-threatening illness or injury,
 - Resulted in permanent impairment of a body structure or a body function,
 - Required hospitalization or prolongation of existing hospitalization,
 - Resulted in medical or surgical intervention to prevent permanent impairment to body structure or a body function;
- 3) Led to fetal distress, fetal death or a congenital abnormality or birth defect.

Note: A planned hospitalization and/or medical intervention for pre-existing conditions, or a procedure required by the protocol, without serious deterioration in health, is not considered to be a serious adverse event.

As MONOVISC is an approved device for the treatment of OA in the knee, certain AE are known to be associated with single intra-articular knee injections of MONOVISC. These can be found in the MONOVISC Package Insert⁴. These events are expected to be similar for hip injections; however, risks may be elevated in the present study since the protocol calls for two injections of MONOVISC rather than one injection. In the clinical trial for MONOVISC, adverse events that were related to the injection treatment were the following and are considered Anticipated AE:

- injection site pain/swelling;
- joint stiffness / swelling / effusion;
- arthralgia, or aggravated osteoarthritis;
- pain in extremity;
- synovitis;

- contusion;
- subcutaneous nodule;
- Baker's cyst.

AE will be summarized as followings with the number of events and the number and proportion of subjects with events. This analysis will be conducted using the Safety Analysis Set:

- All AE;
- All Device or Procedure Related AE (defined as possible, probable, or related);
- All AE leading to treatment discontinuation;
- All AE by Severity;
- All AE by Relationship (to investigational products or any protocol mandated procedures);
- All SAE;
- All UADE;
- All Anticipated AE.

13.5.2 Radiographs

Radiographs are not collected post-baseline and will therefore not be summarized.

13.5.3 Study Specific Data

No additional study specific data will be analyzed.

13.6 Site Heterogeneity

For the primary endpoint data at 26 Weeks, a 2-way ANOVA test with interaction term will be conducted to confirm the homogeneity of 26 week data across sites.

13.7 Poolability Analysis

To assess the poolability of outcomes across sites, a sensitivity analysis to assess the homogeneity of outcomes across sites will be conducted on the primary endpoint. The analysis is identical to the primary analysis of the primary endpoint (a longitudinal model of WOMAC A1 pain change from baseline over time) with the exception of the inclusion of 2 additional fixed effects: Site and Treatment by Site interaction. Sites with fewer than 10 subjects will be pooled into a single small site grouping while others will remain unique in the model. If the overall site effect is determined to be significant, a stratified analysis will replace the primary analysis of the primary and secondary endpoints. All analyses specified for these endpoints will be conducted by site.

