11.10 Analysis Plan

All statistical processing will be performed using SAS® Version 9.2 or higher, unless otherwise noted. A separate Statistical Analysis Plan (SAP) document that provides greater detail on data derivations and the analyses to be performed will be developed within 90 days after the first patient is enrolled.

Summary tables will be provided for subject demographics and baseline variables for the Safety Analysis Set, the As Treated Analysis Set at 26 weeks, and the Per Protocol Analysis Set at 26 weeks. Safety endpoints (adverse events) will be summarized on the Safety Analysis Set. Effectiveness endpoints will be summarized at each protocol-specified evaluation time point on the Per Protocol Analysis Set for the time point. Analyses will be conducted on pooled data from all sites. For the primary endpoint data at 26 weeks, a 2-way ANOVA test with interaction term will be conducted to confirm the homogeneity of 26 week data across sites. The primary endpoint analysis will be conducted with a longitudinal model on the MITT Analysis Set using PROC MIXED and an antedependence covariance structure to model the correlation between visits. A supportive analysis of the primary endpoint analysis will be conducted on the Per Protocol Analysis Set for Longitudinal Analysis with the same PROC MIXED model.

Descriptive statistics for dichotomous/categorical variables will include the number and percentage of subjects. Fisher's exact test 2-sided *p*-values will be provided for the comparison of dichotomous variables, including adverse event rates, to facilitate clinical judgment. Descriptive statistics for continuous variables will include the number of subjects, mean, standard deviation, median, minimum, and maximum. *P*-values for comparing continuous endpoints will be provided to facilitate clinical judgment; these will be 2-sided *p*-values based upon the t-distribution.

If Age, Gender, or pre-injection WOMAC A1 pain score are found to be significantly different (*p*<0.05) across treatment groups in the As Treated Analysis Set at 26 weeks, then an ANCOVA sensitivity analysis will be conducted for the primary endpoint analysis (on the MITT Analysis Set, with Age, Gender, and pre-injection WOMAC A1 pain as covariates).

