6.1 Control of Type 1 Error

Family-wise control of Type I Error across all primary and secondary endpoints will be accomplished using the following gatekeeping strategy which is depicted in Figure 1.

If the study is successful and the primary endpoint analysis demonstrates a statistically significant difference (favoring MONOVISC vs. Saline) at 26 Weeks, then we will test the WOMAC A1 change from baseline at 16 Weeks for a significant difference (favoring MONOVISC vs. Saline). If this is successful, we will test the difference at 8 Weeks; if this is successful, we will test the difference at 4 Weeks; and if this is successful, we will test the difference at 2 Weeks. At any point, if one of these comparisons fails to be statistically significant, then we will cease further testing in the specified order. Each of these tests will be conducted utilizing the primary endpoint analysis on the Modified Intent to Treat Analysis Set for Longitudinal Analysis. We will test each of the secondary endpoints with a 2-sided p-value against threshold of 0.05 (a 2-sided 5% alpha) with no further adjustment for multiplicity.

Further detail of the hypotheses tested is found in Section 10.

Figure 1 Primary and Secondary Gatekeeping Procedural Flow

Note: The hypothesis tests indicated above are to be performed on the endpoints which we have specified as primary and secondary, WOMAC A1 change from baseline at 26 (primary) weeks and also at 2, 4, 8, and 16 weeks.

7 Interval Windows

The study windows are presented in the Time and Events Schedule (CSP Section 1.1).

For analysis purposes, the baseline/screening evaluation is to be done within 30 days prior to the first injection; the first injection is considered to be day 0. The 2, 4, 8, 16 and 26 Week visits will occur in the time intervals (days) indicated in Table 2, below.

Table 2 Study Interval Windows

Analysis Visit Label	Nominal Study Visit	Study Interval
Baseline	Baseline/Screening	-30 to 0
2 Week	Day 14 ± 7 days	11 to 17
4 Week	Day 28 ± 7 days	21 to 35
8 Week	Day 60 ± 14 days	46 to 74
16 Week	Day 120 ± 14 days	105 to 134
26 Week	Day 180 ± 14 days	159 to 201

Note:

Day 0 is defined as the Study Day of first injection.

Baseline is defined as the last non-missing assessment prior to first injection.

Baseline must occur no more than 30 days after Screening.

8 Handling of Missing Data

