9.4 Safety

Safety of the therapy will be assessed by comparing the incidence of adverse events in the MONOVISC vs. Saline group through 26 Weeks post-injection, including AEs that occur during injection.

10 Hypotheses

The primary endpoint analysis will be conducted to demonstrate that the mean WOMAC A1 walking pain score change from baseline for MONOVISC is significantly better than the mean WOMAC A1 walking pain score change from baseline for Saline at 26 Weeks after the first injection. The null (H_0) and alternate (H_A) hypotheses for this test of superiority are as follows:

$$H_0: \mu_{\text{MONOVISC}} \geq \mu_{\text{Saline}}$$

$$H_A: \mu_{\text{MONOVISC}} < \mu_{\text{Saline}},$$

where μ_{MONOVISC} is the mean WOMAC A1 walking pain score change from baseline for MONOVISC at 26 Weeks, and μ_{Saline} is the mean WOMAC A1 walking pain score change from baseline for Saline at 26 Weeks.

Decision Criterion: The primary endpoint analysis will be based upon a longitudinal model as described in Section 13.4.1. The adjusted means from this longitudinal model at 26 Weeks will be compared between treatment groups. The decision will be made to reject the null hypotheses and conclude the alternative if:

1. WOMAC A1 walking pain change from baseline adjusted mean for the MONOVISC group is less than the WOMAC A1 walking pain change from baseline adjusted mean for the Saline group and,
2. The two sided p-value for the comparison of these adjusted means is less than 0.05. Or, equivalently, if the entire 2-sided 95% confidence interval for the WOMAC A1 walking pain change from baseline adjusted mean between treatment group difference (MONOVISC minus Saline), based upon the longitudinal model estimates, is less than 0.

11 Analysis Sets

A detailed accounting of all enrolled Subjects will be documented with the following analysis sets.

Intent to Treat (ITT) Analysis Set: The ITT Analysis Set consists of all subjects who are enrolled into the study. Subjects in the ITT Analysis Set but in whom treatment is not attempted with either MONOVISC or Saline will be listed along with the reason for not being treated.

Safety Analysis Set: The Safety Analysis Set consists of all randomized subjects who were enrolled into the study and in whom treatment was attempted with either MONOVISC or Saline. Subjects will be analyzed according to the treatment which was attempted.

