  groupweights=(2 1)
  power= .8
  alpha=0.05
```

13 Analysis Plan

All statistical processing will be performed using SAS® Version 9.2 or higher, unless otherwise noted.

Descriptive statistics for dichotomous/categorical variables will include the number and percentage of subjects. Fisher's exact test 2-sided p-values will be provided for the comparison of dichotomous variables, including adverse event rates, to facilitate clinical judgment. Descriptive statistics for continuous variables will include the number of subjects, mean, standard deviation, median, minimum, and maximum. P-values for comparing continuous endpoints will be provided to facilitate clinical judgment; these will be 2-sided p-values based upon the t-distribution.

Summary tables will be provided for subject demographics and baseline variables for the Safety Analysis Set, the As Treated Analysis Set at 26 Weeks, and the Per Protocol Analysis Set at 26 Weeks. Safety endpoints (adverse events) will be summarized on the Safety Analysis Set. Effectiveness endpoints will be summarized at each protocol-specified evaluation time point on the Per Protocol Analysis Set for the time point. Analyses will be conducted on pooled data from all sites unless the analysis described in Section 13.7 determines sites are not poolable.

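### SAP 13.7 lets a significant site effect replace the primary analysis with analyses by site, which leaves no overall test; the treatment-by-site term decides nothing

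*SAP*

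**What the plan says.** SAP 13.7 describes a sensitivity analysis: the primary longitudinal model with Site and Treatment by Site added as fixed effects. On site size it says "Sites with fewer than 10 subjects will be pooled into a single small site grouping while others will remain unique in the model". It then gives its only decision rule: "If the overall site effect is determined to be significant, a stratified analysis will replace the primary analysis of the primary and secondary endpoints". The replacement is described in one further sentence: "All analyses specified for these endpoints will be conducted by site".

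SAP 13 confirms that the rule is meant to operate: "Analyses will be conducted on pooled data from all sites unless the analysis described in Section 13.7 determines sites are not poolable". SAP 13.6 adds a separate check, in which "a 2-way ANOVA test with interaction term will be conducted to confirm the homogeneity of 26 week data across sites", with no consequence attached.

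Three other places assume one overall analysis:

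- SAP 10 defines success through the 13.4.1 model: "The adjusted means from this longitudinal model at 26 Weeks will be compared between treatment groups".
- SAP 6.1, on the secondary sequence: "Each of these tests will be conducted utilizing the primary endpoint analysis on the Modified Intent to Treat Analysis Set for Longitudinal Analysis".
- Protocol 11.10, with no exception: "Analyses will be conducted on pooled data from all sites".

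SAP Table 1, which lists substantive changes from the protocol, does not mention the switch.

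**The concern.** There are two separate problems.

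**The trigger.** On its natural reading, an overall site effect is the site main effect, that is, a difference between sites in average pain change. Such differences can arise from case mix, expectation or local practice, and they say nothing about whether MONOVISC works differently from site to site. The term that does address this, Treatment by Site, is fitted in 13.7, and a site interaction is tested again in 13.6. Neither result leads to any action.

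**The replacement.** If the analyses are done separately by site, the SAP gives no weights, no combined estimate, no overall p-value and no success rule. The criterion in SAP 10 cannot be evaluated and the sequence in SAP 6.1 cannot start. A feature of the data unrelated to treatment could therefore remove the trial's only powered confirmatory test. The word *stratified* could instead mean one combined, site-adjusted comparison, but the sentence that follows points the other way.

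**Working it through.** **Inputs from the documents.** Difference 0.6 NRS, SD 2.2 in both arms, 2:1 allocation, two-sided 5% level, 318 + 159 = 477 evaluable (SAP 12). Up to 25 sites (SAP 4) or up to 40 (Protocol 1.0). **Assumed:** the site intraclass correlation (ICC) and the distribution of site sizes, because the documents give neither.

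**1. The plan's own figure.** SE = 2.2 × √(1/318 + 1/159) = 0.2137. Noncentrality = 0.6 / 0.2137 = 2.81 on 475 df. Noncentral-t power = 80.0%, so the SAP's sample size is reproduced for one overall test.

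**2. Power if the analysis is done by site.** 477/25 ≈ 19 per site, about 13/6. 477/40 ≈ 12 per site, about 8/4. Power is for a significant result favouring MONOVISC.

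| Arms | SE | Noncentrality | df | Power | Difference needed for 80% power |
|---|---|---|---|---|---|
| 13/6 | 1.086 | 0.553 | 17 | 7.5% | 3.2 NRS |
| 8/4 | 1.347 | 0.445 | 10 | 6.0% | 4.2 NRS |
| 20/10 | 0.852 | 0.704 | 28 | 10.0% | – |
| 40/20 | 0.602 | 0.996 | 58 | 16.3% | – |

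The 8/4 row ignores pooling of small sites. With unequal sites (gamma(2) size weights, assumed) and sites under 10 merged as 13.7 directs, 25 sites become about 19 groups and 40 become about 22. Mean group power is then 8.9% and 8.2%, and the best-powered group averages 15.6% and 23.8%.

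**3. How often the rule fires when the treatment effect is the same at every site.** For equal sites of size n at one visit, the site F test is significant with probability P(F > F_crit / k), where k = 1 + n × ICC/(1 − ICC). With 25 sites, n = 477/25 = 19.08 and F_crit(24, 452) = 1.54. At ICC 0.05, k = 1 + 19.08 × 0.05/0.95 = 2.00, so the threshold is 1.54/2.00 = 0.77 and the probability is 78%. With 40 sites, n = 11.925, F_crit(39, 437) = 1.43 and k = 1.63, which gives 68%.

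The simulated columns use unequal sites with small ones pooled, 26-week data only, the F test of Site in a model that also holds Treatment and Treatment by Site, and 2,500 runs per setting.

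| ICC (assumed) | Formula, 25 sites | Formula, 40 sites | Simulated, 25 sites | Simulated, 40 sites |
|---|---|---|---|---|
| 0 | 5% | 5% | 6.0% | 4.4% |
| 0.01 | 16% | 13% | 15.4% | 12.9% |
| 0.02 | 33% | 25% | 27.6% | 23.3% |
| 0.05 | 78% | 68% | 69.3% | 60.8% |

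An ICC of 0.05 is a between-site SD of only 2.2 × √0.05 = 0.49 NRS. In the same simulations the interaction test was significant in 4.1–5.7% of runs, as it should be.

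**4. The opposite error.** In a simulation of 25 equal sites with a true treatment-by-site SD of 1.0 NRS and no separate site variance, the interaction was significant but the site term was not in about 22% of 2,000 runs. The rule would not fire in those trials.

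**5. If the replacement were one combined site-adjusted test.** Switching to it on the site test gives power of 79.0–80.2%. False positives favouring MONOVISC at ICC 0.05 are 2.6% (25 sites) and 2.3% (40 sites), against a nominal 2.5%.

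**6. If the gap were filled loosely.** The SAP does not propose counting any one site's significant result as success. That rule would give a false-positive risk of 1 − 0.975^25 = 47% or 1 − 0.975^40 = 64%.

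**The case against.** The severe result depends on one of two readings. *Stratified analysis* ordinarily means one comparison stratified by a factor, and on that reading step 5 shows almost no harm. *Overall site effect* is undefined and could mean a joint test of both site terms, in which case the interaction would count. The ambiguity could also be resolved blind, in a SAP revision or in the table shells due before database lock. Finally, the firing rates rest on assumed ICCs and one visit, whereas the SAP's test uses five.

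Much of this is fair. The benign reading is possible, the frequency is uncertain, and nothing forces the choice of reading to wait until outcome data have been seen. The objection still does not rescue the rule:

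- The by-site sentence favours separate analyses, and no combined estimate is named anywhere.
- A joint test also fires often: in about 48–64% of simulated trials at ICC 0.05 with no true interaction.
- Even with no site differences at all, the rule fires in about 5% of trials by chance.

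**Conclusion.** The concern holds and should be fixed before the final analysis. SAP 13.7 states a rule that, followed as written, replaces a test with 80.0% power by separate site comparisons with power of roughly 6–9% on average. It leaves SAP 10 and SAP 6.1 without a result to act on, and it departs from Protocol 11.10. These power figures follow from the SAP's own design inputs plus assumed site sizes. The firing rate is less certain: 4–6% with no site differences, 13–15% at ICC 0.01, 23–28% at 0.02 and 61–69% at 0.05, all conditional on assumed ICCs and a one-visit approximation. If a single site-adjusted test was intended, the loss is negligible, but the choice of analysis would still hang on a term that does not bear on the treatment comparison.

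**What to change.** In SAP 13.7, delete the replacement rule and the by-site sentence. In SAP 13, delete the clause that makes pooling depend on 13.7. State that the pooled longitudinal model in 13.4.1 is the only confirmatory analysis of the primary and secondary endpoints. Report three things as supportive results that cannot change the primary test: a site-adjusted version of the model without interaction (small sites pooled), the Treatment by Site test, and site-specific estimates.

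An acceptable alternative is to prespecify, unconditionally, one site-adjusted overall estimate with one p-value as the primary analysis. With equal sites, no pooling of small sites and unstratified allocation, its power at about 477 evaluable is about 78% (25 sites) or 77% (40 sites), against 80% unadjusted.

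The cost is SAP wording, one small supportive model and site-specific estimates that are not planned unconditionally now. No new data are needed. The site count (25 in the SAP, 40 in the protocol) should be reconciled in the same revision.

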13.8 Additional Analyses

The tertiary endpoints will be analyzed as described below:

Walking Pain:

WOMAC A1 score mean change over 26 Weeks will be analyzed using the same longitudinal model and analysis sets as the primary endpoint. The mean changes in WOMAC A1 over 26 Weeks will be reported as the least squares means for treatment and the between treatment group difference will be estimated.

WOMAC A1 score at the 2, 4, 8, 16 and 26 Week time points will be analyzed with a similar longitudinal model to that of the primary endpoint; however, the dependent variable will become the observed value (rather than change).

WOMAC A1 score change from baseline area under the curve (AUC) will be analyzed using the trapezoidal rule to calculate the AUC for each subject. Data will be reduced to a single AUC result per subject then an appropriate between-treatment 2 sample

t-test will be conducted. If the AUC appear non-normal, then an additional t-test comparison will be done on log-transformed data.

Pain:

WOMAC A score at the 2, 4, 8, 16 and 26 Week time points will be analyzed with a similar longitudinal model to that of the primary endpoint; however, the dependent variable will become the observed value (rather than change) for the entire pain subscale.

WOMAC A score change (improvement) from baseline at the 2, 4, 8, 16 and 26 Week time points will be analyzed with a similar longitudinal model to that of the primary endpoint; however, the dependent variable will become the change from baseline for the entire pain subscale.

Pain, Stiffness and Physical Functioning:

Summary statistics for the total WOMAC score at the 2, 4, 8, 16 and 26 Week time points will be provided.

Summary statistics for the total WOMAC score change (improvement) from baseline at the 2, 4, 8, 16 and 26 Week time points will be provided.

Disease Activity:

Patient Global Assessment (PGA) at the 2, 4, 8, 16, and 26 Week time points will be summarized as tallies in each ordinal category (0 through 10).

Health Outcomes:

Summary statistics for the Physical and Mental Composite scores of the SF-12 outcomes at study defined time-points will be provided.

Rescue Medicine Consumption:

Acetaminophen use from baseline through 26 Week will be analyzed by presenting the incidence of use by study time point and overall. Difference between treatment groups will be assessed using fisher's exact test. In addition, an analysis will be conducted to provide a summary of the dose (total over the entire study period and in the interval prior to the visit).

OMERACT-OARSI Responder Rate:

The response rate will be summarized at each study time point with counts and proportions.

14 Plans for Interim Analysis (IA)

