6.3 Study Population

This study will be restricted to adult patients with mild to moderate hip osteoarthritis, as measured by Kellgren/Lawrence score. Up to 560 patients will be treated in a 2:1 randomization scheme. Such patients have been shown to derive the greatest benefit from HA therapy in previous studies of patients with knee OA, and are the indicated patient population for currently marketed HA therapies. Only patients with K-L Grades 2 and 3 hip OA will be included in the trial, such that beginning and end stage OA patients are excluded. Also, only patients reporting NRS walking pain of ≥ 4 and ≤ 8 will be included. These pain states were chosen to exclude patients with only minimal pain that can be addressed with conservative therapy, as well as those with end stage disease that are not likely to respond to HA therapy.

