The primary efficacy endpoint analysis will be conducted on the MITT Analysis Set, which consists of all primary endpoint data on all As Treated (AT) subjects (regardless of whether or not there were protocol deviations associated with the data) for the 2, 4, 8, 16 and 26 week visits. In this MITT Analysis Set, missing primary endpoint data for the 26 Week visit will be imputed with multiple imputation methodology using SAS PROC MI with the regression method and a monotone missing data pattern.

No imputation of missing data will be performed for visits other than the 26 Week visit.

9 Primary and Secondary Endpoints

The primary and secondary endpoints are derived from the Western Ontario and McMaster Universities Arthritis Index (WOMAC), which is widely used in the evaluation of Hip and Knee Osteoarthritis. The WOMAC is available in over 65 languages and has been linguistically validated. It is a self-administered questionnaire consisting of 24 items divided into 3 subscales, A, B, and C: A) Pain (5 items), B) Stiffness (2 items), and C) Physical Function (17 items). The overall WOMAC score is determined by summing the scores across the 3 subscales and the score ranges include 0–24 (derived from the NRS scale). Higher scores on

the WOMAC indicate worse pain, stiffness, and functional limitations. Specific scoring details will be provided in the table shells document referenced in Section 15.

The WOMAC A is the pain subscale of the WOMAC questionnaire. Again, response options for individual questions are 0 through 10, where 0 indicates no pain and 10 indicates worst possible pain. The WOMAC A pain subscale scores ranges are 0-50 NRS.

WOMAC A1 is the first question of the WOMAC A and specifically addresses pain during walking. Response options are 0 through 10 NRS, where 0 indicates no pain and 10 indicates worst possible pain.

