9.3 Tertiary Endpoints

The following are considered tertiary endpoints, and will be summarized in tables of summary statistics:

Walking Pain:

WOMAC A1 score mean change over 26 Weeks.WOMAC A1 score at the 2, 4, 8, 16 and 26 Week time points.

WOMAC A1 score change from baseline area under the curve (AUC).

Pain:

WOMAC A score at the 2, 4, 8, 16 and 26 Week time points.

WOMAC A score change (improvement) from baseline at the 2, 4, 8, 16 and 26 Week time points.

Pain, Stiffness and Physical Functioning:

Total WOMAC score at the 2, 4, 8, 16 and 26 Week time points.

Total WOMAC score change (improvement) from baseline at the 2, 4, 8, 16 and 26 Week time points.

OMERACT-OARSI Responder Rate:

The OMERACT-OARSI responder rate will be derived from the WOMAC A (Pain) and C (Function) subscale scores and PGA score, as discussed in Pham (2003)¹.

Response will be determined at each visit and with the available data (no imputation of missing data will be performed to assess response). To be considered a Responder at a visit either criteria 1 or 2 must be met:

1. WOMAC A (Pain) or WOMAC C (Function) relative change from baseline $\geq 50\%$ and an absolute change ≥ 20
2. Improvement in at least 2 of the following:
 - WOMAC A (Pain) Score: a relative change from baseline $\geq 20\%$ and an absolute change from baseline ≥ 10 .
 - WOMAC C (Function) Score: a relative change from baseline $\geq 20\%$ and an absolute change from baseline ≥ 10 .
 - Patient's global assessment (PGA): a relative change from baseline $\geq 20\%$ and absolute change from baseline ≥ 10 .

In 1 and 2 above, relative change will be calculated as:

$100\% \times \frac{\text{Score at Visit} - \text{Baseline Score}}{\text{Baseline Score}}$ and absolute change will be calculated as:

Score at Visit – Baseline Score.

Disease Activity:

Patient Global Assessment (PGA) at the 2, 4, 8, 16, and 26 Week time points.

Health Outcomes:

Physical and Mental Composite scores of the SF-12 outcomes at study defined time-points

Rescue Medicine Consumption:

Acetaminophen use from baseline through 26 Weeks.

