14.2 Efficacy and Safety Variables

The efficacy variable of interest for the IA is the WOMAC A1 pain score change from baseline difference between treatment groups (MONOVISC minus Saline), expressed as an improvement.

The assessment of Safety is not an explicitly stated objective, however, sufficient safety data is required to inform a decision concerning membership in the IA PP Analysis Set at Week 26.

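### The back-up AUC test in SAP 13.8 takes the log of a signed change-from-baseline area, and the SAP gives no rule for subjects whose area is zero or negative

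*SAP*

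**What the plan says.** SAP 9.3 lists the AUC of WOMAC A1 change from baseline among the tertiary endpoints. SAP 13.8 gives the method: "using the trapezoidal rule to calculate the AUC for each subject", then a two-sample t-test on the single value per subject, and finally the back-up rule, "If the AUC appear non-normal, then an additional t-test comparison will be done on log-transformed data".

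The direction of the variable has to be pieced together:

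- SAP 9 defines WOMAC A1 on 0 to 10, "where 0 indicates no pain and 10 indicates worst possible pain", so improvement lowers the score.
- SAP 10 requires for success that the "WOMAC A1 walking pain change from baseline adjusted mean for the MONOVISC group is less than" the saline value, so the better arm has the smaller change.
- The only written formula for absolute change, given in SAP 9.3 for the responder criteria, is visit score minus baseline score.
- SAP 14.2 describes the interim variable as "expressed as an improvement". Nothing applies that scale to the AUC.

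SAP 13.8 states no sign for the AUC, no constant to be added before the log, and no handling of values at or below zero.

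**The concern.** A log transform suits a positive, right-skewed variable. A change-from-baseline area is neither positive by construction nor bounded at zero. Protocol 6.3 states that "only patients reporting NRS walking pain of ≥ 4 and ≤ 8 will be included". If baseline WOMAC A1 falls in that same range, change at a visit can run from −8 to +6, so the area can take either sign.

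The log therefore does not exist for part of the sample, and which part depends on outcome. Unless someone improvises a rule, a t-test on logged values would compare arms within a subset selected by how subjects fared, with different fractions kept in each arm. The p-value would no longer address the randomised comparison. The alternative is to choose an offset or a sign once the data are in hand, which is the kind of decision a SAP is meant to settle in advance.

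**Working it through.** **Inputs from the documents.** Between-arm difference 0.6, SD of change 2.2 (stated for week 26), 2:1 allocation, two-sided 5% and 80% power (SAP 12 and 6). Nominal visit days 14, 28, 60, 120 and 180 (Protocol 1.1).

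**Assumptions, not in the documents.** SD 2.2 at every visit; mean change constant over visits; saline mean change from +0.4 to −2; equal correlation ρ between visits of 0.3, 0.5 or 0.7; change set to 0 on day 0.

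**The plan's own figure.** The SAP gives no figure for the AUC, so the check on inputs is the sample size. Control n = (1 + 1/2) × 2.2² × (1.960 + 0.842)² / 0.6² ≈ 158.3, rounded up to 159. With 318 active this gives the stated 477.

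**Trapezoid weights.** On days 0, 14, 28, 60, 120 and 180 the five visits carry weights 14, 23, 46, 60 and 30 (sum 173). Examples:

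- −2 at every visit: −2 × 173 = −346, no log.
- No change at any visit: 0, no log.
- +1 at every visit: +173, log exists.
- Changes −3, −3, −1, +1, +2: −42 − 69 − 46 + 60 + 60 = −37, no log.

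**Share with a negative area, improvement coded as negative.** The sum of squared weights is 7,341 and 173² = 29,929, a ratio of 0.245. The SD of the time-weighted mean change is 2.2 × √(ρ + (1 − ρ) × 0.245), that is 1.51, 1.74 and 1.93 for ρ = 0.3, 0.5 and 0.7. In each arm P(AUC < 0) = Φ(−mean / SD), and the pooled value is (saline + 2 × MONOVISC) / 3.

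Worked case: saline mean −1, MONOVISC −1.6, ρ = 0.5. Saline Φ(1/1.74) = 0.718; MONOVISC Φ(1.6/1.74) = 0.822; pooled (0.718 + 1.644) / 3 = 0.787.

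| Saline mean change | ρ = 0.3 | ρ = 0.5 | ρ = 0.7 |
|---|---|---|---|
| +0.4 | 50% | 50% | 50% |
| 0 | 60.3% | 59.0% | 58.1% |
| −1 | 81.9% | 78.7% | 76.3% |
| −2 | 94.1% | 91.4% | 89.0% |

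Starting the trapezoid at day 14 instead of day 0 hardly matters: at ρ = 0.5 the last three rows become 59.0%, 78.6% and 91.2%.

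**Simulation with integer scores.** Using 0–10 scores, baselines of 4 to 8 and ρ = 0.5, the negative shares are 58.9%, 78.6% and 91.2% for saline means 0, −1 and −2. Exact zeros add 0.2 to 0.4 percentage points. Of 477 evaluable subjects, about 194, 101 and 41 would have a log. At saline mean −1, 18% of MONOVISC and 28% of saline subjects remain. The difference in time-averaged change among them is about −0.1, against the −0.6 built in.

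**Sign reversed.** If the area were coded as improvement, the log would be missing for about 41% of subjects at saline mean 0 and 21% at saline mean −1 (ρ = 0.5).

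**The case against.** The strongest reply is that very little depends on this test. The AUC is tertiary, the log test is both conditional and additional, and the untransformed t-test is reported regardless. With several hundred subjects and a bounded score, that t-test is reasonable even with moderate skew. The gatekeeping in SAP 6.1 covers only the primary and secondary endpoints. All of this stands and limits the point to a minor one.

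The second reply is that the sign is less settled than it looks. SAP 9.3 and 13.8 label WOMAC A and total WOMAC changes as improvement. SAP 14.7 treats a MONOVISC-minus-saline difference above 0.4 as favouring MONOVISC. The responder rule uses visit minus baseline but requires changes of at least +10 or +20, which fits improvement only if improvement is positive. This stands too. A reader might infer that the log test would certainly run on patients who got worse, but that holds only under one coding, although the more natural one. What does not depend on the coding is that some subjects have no log value.

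Third, the SAP does not tell anyone to drop subjects with a non-positive area; it is silent. Exclusion is what a literal run would produce, not a stated rule.

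Three possible rescues do not work. Absolute change in SAP 13.4.1 could be read as a modulus, but SAP 9.3 uses the term for change in score units, with a signed formula. The shells document named in SAP 15 is to hold scoring algorithms, but this transform is not deferred to it. Logging raw scores before forming the area would also fail, because 0 is a valid score.

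**Conclusion.** The rule is wrong as written. A t-test on the log of this area cannot be carried out on all subjects under either sign convention, and the SAP does not say what to do with the rest.

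A reader might infer that the test is undefined for most of the trial. The documents do not establish this, because they give no within-arm mean change. It is likely rather than certain: with improvement negative and the assumptions listed, more than half of subjects have a negative area unless saline worsens by 0.4 or more, which is the point where the pooled mean change is zero. The correlation moves the share by only 2 to 6 percentage points; the assumed saline change drives it.

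A reader might also infer that the AUC endpoint or the trial's main conclusions are compromised. They are not. The primary test, the gated secondary tests and the untransformed AUC t-test are unaffected. Severity is low. The existence of the defect is certain; its size depends on assumptions.

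**What to change.** The simplest change is to delete the log-transform sentence from SAP 13.8 and keep the t-test on the untransformed AUC.

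If a check on non-normality is wanted, replace the sentence with a sensitivity analysis fixed in advance, on the untransformed AUC and including every subject who has one. Two suitable choices:

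- a bootstrap confidence interval for the difference in mean AUC, which keeps the same target as the t-test; or
- a Wilcoxon rank-sum test with a Hodges–Lehmann interval, noting that this targets a location shift and not the mean difference.

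Running it regardless of how the AUC looks would also remove the undefined trigger. State the sign convention for the AUC in the same place. Reversing the sign alone is not enough, because unchanged and worsened subjects would still have no log.

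Cost: one or two SAP sentences and a few lines of code, with no new data and no effect on sample size. It should be done before unblinding, so that no offset or sign is chosen with results in view.
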